5.2 Assessment for Toxicities

Any subject who receives treatment on this protocol will be evaluable for toxicity. Each subject will be assessed for the development of toxicity according to the Time and Events Table (Table 3). Toxicity will be assessed according to the CTCAE v. 5.

All drug administration will be performed by nurses in the inpatient unit. Routine vital sign measurement will be performed and all adverse events (AEs) will be recorded. Toxicities will be classified as AEs probable, possible, unlikely or unrelated to uproleselan.

5.2.1

Evaluating for progression to Acute Respiratory Failure

- Reduction in the progression to acute respiratory failure [Time Frame: 15 days].
- Patients with a baseline PaO₂/FiO₂ \geq 200: progression of respiratory failure is defined by:
 - a. severe gas transfer deficit (PaO₂/FiO₂ < 200).
 - b. persistent respiratory distress while receiving oxygen (persistent marked dyspnea, use of accessory respiratory muscles, paradoxical respiratory movements).
- The rate will be calculated as the proportion of patients who experienced at least one of the events above by day+15 from treatment start.
- Overall survival and all-cause mortality (day 15, day 28).
- Time to improvement in oxygenation for at least 48 hours. Improvement in oxygenation is defined as an increase in PaO₂/FiO₂ of 50 (or greater) compared to the nadir of PaO₂/FiO₂.
- Number of patients requiring mechanical ventilation, if not on mechanical ventilation at study entry.
- Change in the WHO COVID-19, “8-point ordinal scale” from study entry to day 28 (Table 1). To be assessed on day 3, day 8, day 15, day 28.
- Duration of hospitalization and duration of ICU care.
- Toxicity assessment (including incidence of grade 3-5 hemorrhagic events).
- Change in D-dimer [Time Frame: baseline, study day 3, day 8, day 15, and day 28]. Changes in plasma D-dimer level compared with baseline at enrollment.
- Decrease or Change in IL-6:IL-10 ratios.

- Free-Days- at day 28
Oxygen
Ventilator
Vasopressor
ICU
Hospitalization

Table 1: WHO Ordinal Scale Ordinal Score

Patient State	Descriptor	Score
Ambulatory	No limitation of activities	1
	Limitations of activities	2
Hospitalized (mild disease)	No oxygen therapy	3
	Oxygen by mask or nasal prongs	4
Hospitalized (severe disease)	Non-invasive ventilation or high-flow oxygen	5
	Intubation and mechanical ventilation	6
	Mechanical ventilation + additional organ support – pressors, RRT, ECMO	7
Dead	Death	8

Exploratory Endpoints

- Soluble E-selectin and P-selectin levels compared with baseline at enrollment.
- Thrombosis free days (clinically defined) at day 28.
- Change in other cytokine levels, endothelial or leukocyte activation (day 1, 15, 28) in IL-6, IL-10, TNF-alpha and Angiopoietin-2.

5.3 Concomitant Medications/Treatments

Table 3: Standard of Care Treatments⁴⁰

1. Supplemental oxygen, escalate to heated high flow nasal cannula, noninvasive ventilation, endotracheal intubation and mechanical ventilation as needed.
2. Conservative fluid management strategy.
3. Dexamethasone 6mg (PO or IV) qD for up to 10d (RECOVERY trial, Horby PW et al. ³⁸
4. Remdesivir 200 mg loading dose, then 100 mg daily for up to 9 additional days (ACTT-1 Study, Beigel JH et al. ³⁹
5. Convalescent plasma for compassionate use.
6. Other medical management as recommended by Infectious Disease Consultants.
7. Management of septic shock.
8. ICU admission as required.

5.4 Duration of Therapy

Each subject in the treatment arm will receive one dose of uproleselan every 12 hours (12 hours apart optimally; acceptable range 10-14 hours) on treatment days 1-7.

5.5 Duration of Follow-Up

Subjects will be followed for 28 days. Subjects with treatment-emergent adverse events will be followed until resolution or stabilization of the adverse event.

5.6 Off Study Criteria

Subjects can be taken off study at any time at their own request, or they may be withdrawn at the discretion of the investigator for safety, behavioral, or administrative reasons. If possible, subject will follow protocol procedures related to safety analysis. The reason(s) for discontinuation from study will be documented and may include:

- Subject withdraws consent (termination of treatment and follow-up).
- Loss of ability to freely provide consent through imprisonment or involuntary incarceration for treatment and follow-up.
- Subject is unable to comply with protocol requirements.
- Treating physician judges continuation on the study would not be in the subject's best interest.
- Drug-related toxicity or adverse event, which contraindicates continuation in the study
- Subject becomes pregnant: If patient pregnancy results become known during treatment period, pregnancy should be followed and specific monitoring as per NIH guidelines conducted.⁴¹
- Termination of the study by The University of Michigan or GlycoMimetics Inc.
- Subject completes protocol treatment and follow-up criteria.

5.7 Subject Replacement

Subjects will be replaced in this study if they are removed.

6 STUDY PROCEDURES

6.1 Screening Procedures

Assessments performed exclusively to determine eligibility for this study will be done only after obtaining informed consent. Hematology, serum chemistry or coagulation assessments performed for clinical indications will be used from hospital admission. All screening procedures, unless noted above, must be performed within 48 hours of subject's requirement of supplemental oxygen for diagnosis of COVID pneumonia and prior to enrollment unless otherwise stated. The screening procedures include:

- Informed Consent
- Demographics
- Age, gender, race, ethnicity
- Complete medical and surgical history
- Review subject eligibility criteria
- Review and record prior and concomitant medications/therapies
- Physical exam including vital signs, height and weight

- Vital signs include temperature, pulse, respirations, blood pressure
- Hematology, serum chemistry and coagulation studies
- Serum pregnancy test (for females of child-bearing potential)

6.1.1 Procedures during Study Drug Treatment Visits

If a laboratory parameter has been obtained within 48 hours prior to study enrollment, it does not need to be repeated for study purposes and will be considered the *baseline* value. Following the last day of study, no further “study related” blood tests will be obtained.

Guidelines for monitoring hematologic and coagulation parameters were derived from Thachil, J., et al., *ISTH interim guidance on recognition and management of coagulopathy in COVID-19*. *J Thromb Haemost*, 2020. **18**(5): p. 1023-1026.⁴²

- **Pulmonary Indices:** Pulmonary parameters will be recorded daily for subjects from the time of study entry to cessation of study drug therapy. Pulmonary assessment will include a subject’s current level of supplemental oxygen support (%FiO₂), current modality of support (mechanical ventilation, BiPaP, CPAP, nasal cannula, or none), and the results of any chest radiographs (if performed) that day. For patients that remain hospitalized on day 15 or 28 of study, pulmonary indices will also be made at that time point. Blood gas values will be obtained as clinically indicated. Scoring from the WHO COVID Ordinal Scale (Table 1) will be determined as indicated by study investigators or study coordinators.
- **Hematologic parameters:**
A complete blood count including platelets (CBCP) should be obtained at baseline (study entry), and daily until cessation of study therapy. Additional blood counts may be obtained as clinically indicated.
- **Chemistries:**
Serum chemistries (Electrolytes, BUN, creatinine, liver panel) should be obtained at baseline (study entry), and daily until cessation of study therapy. Additional chemistries should be obtained as clinically indicated.
- **Coagulation Labs:**
D-dimer, Prothrombin time (PT), activated partial thromboplastin time (aPTT), and serum fibrinogen should be obtained at baseline (study entry). Additional D-dimer, PT, and serum fibrinogen testing may be obtained as clinically indicated.
- **Serologic Cytokine Profiles:** Biomarkers will be drawn on day 0-1 pre-study drug administration, days 1-7, day 15, and day 28. These will be used to measure e-selectin levels and are not for safety labs. Due to current hospital understaffing, blood draws will occur as staffing permits. Missed blood draws will not be counted as protocol deviations.

6.2 Study Schedule of Events

Table 4: Events of the Study

	Baseline	Day 1	Day 2	Day 3	Day 4	Day 5	Day 6	Day 7	Day 8	Day 15	Day 28
Eligibility screen	X										
Informed Consent	X										
Medical history	X										
Physical Exam	X	X	X	X	X	X	X	X			
CBC	X ^a	X	X	X	X	X	X	X			
Chemistries	X ^a	X	X	X	X	X	X	X			
ABG	X ^a										
CXR	X ^b										
Biomarkers ^g	X	X	X	X	X	X	X	X		X	X
D-dimer ^g	X			X					X	X	X
Serum pregnancy test	X ^c										
Pulmonary indices ^d	X	X	X	X	X	X	X	X	X	X	X
Uproleselan		X	X	X	X	X	X	X			
Vital Signs ^e		X	X	X	X	X	X	X			
COVID scale	X			X					X	X	X
AE and follow-up ^f		X	X	X	X	X	X	X	X	X	X

Key: CBC-complete blood count; CXR-chest X ray; ABG-arterial blood gas; BP-blood pressure; HR-heart rate; RR-respiratory rate.

Notes:

- a. Laboratory tests performed within 48 hours prior to study enrollment do not need to be repeated at baseline. CBC should be performed daily (until cessation of study therapy) and should be viewed as standard medical care. Arterial blood gas (ABG) measurements, and chest radiographs should be performed per routine medical care. Venous blood gas may be used when ABG unavailable. Patients should continue to have laboratory tests performed (as indicated above) until cessation of study therapy.
- b. Chest X-Ray (CXR): The CXR does not need to be repeated at baseline, if a CXR was done on admission and revealed bilateral infiltrates.
- c. Pregnancy test: Perform in subjects of child-bearing potential, if not already performed this admission for clinical care reasons.
- d. Pulmonary indices will be recorded daily until cessation of drug therapy, and again at day 8, 15 and 28 (if a patient remains hospitalized at that time). Patients who are discharged prior to day 15 or 28 do not need to have pulmonary indices assessed on day 15 or 28.
- e. Vital signs: heart rate, respiratory rate, blood pressure prior to and upon completion of each infusion.
- f. Adverse Event Reporting and Follow-up: Patients will be assessed for adverse events daily during receipt of study therapy, and for 7 days following completion of study drug therapy, provided they remain hospitalized during this 7-day post-therapy period. In addition, patients will be contacted on day 15 and 28 (± 2 days), to assess their clinical status and any active adverse events at that time. This final assessment can be done virtually, by telephone or electronically (email) if the patient cannot be contacted by phone. No in-person visit is required.
- g. Study blood draws, including D-dimer and biomarkers, will only occur if patient is still hospitalized and as hospital staffing permits (weekends/holidays may not be feasible). No outpatient study blood draws will be performed.

Table 5: Parameters to be Tested for Hematology, Serum Chemistry, and Coagulation Studies

Category	Parameters
Hematology	Hematocrit, hemoglobin, mean corpuscular hemoglobin (MCH), mean corpuscular hemoglobin concentration (MCHC), mean corpuscular volume (MCV), platelets, mean platelet volume, red blood cells (RBCs), white blood cells (WBCs) with complete differential including neutrophils, lymphocytes, monocytes, basophils, eosinophils, immature granulocytes
Serum chemistry	Comprehensive metabolic panel (CMP) to include: total protein, albumin, alkaline phosphatase, ALT/SGPT, AST/SGOT, total bilirubin, BUN, creatinine, estimated glomerular filtration rate (EGFR) (ml/min), electrolytes (sodium, potassium, calcium, chloride, bicarbonate), and glucose
Coagulation	Prothrombin time (PT), international normalized ratio (INR), activated partial thromboplastin time (aPTT), fibrinogen

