2.2 Secondary Objectives

To evaluate if treatment with uproleselan administered intravenously in addition to the best available therapy according to institutional guidelines is able to reduce the progression of acute respiratory failure, in patients with severe COVID-19 pneumonia.

- To evaluate overall survival and all-cause mortality at day 15 and 28.
- To evaluate changes in the COVID ordinal outcomes scale.
- To assess adverse events to evaluate the safety of uproleselan.
- To assess ventilator-free days, ICU-free days, oxygen, vasopressor free days.
- To evaluate changes in D-dimer.

Exploratory Objectives:

- To examine the correlation of plasma soluble E-selectin concentrations with clinical outcomes.
- To examine the correlations of other biomarkers of interest with clinical outcome.

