3.2 Secondary Endpoints

- Reduction in the progression to acute respiratory failure [Time Frame: 15 days for primary endpoint].
- Patients with a baseline PaO₂/FiO₂ ≥ 200: progression of respiratory failure is defined by:
 - a. severe gas transfer deficit (PaO₂/FiO₂ < 200);
 - b. persistent respiratory distress while receiving oxygen (persistent marked dyspnea, use of accessory respiratory muscles, paradoxical respiratory movements);
- The rate will be calculated as the proportion of patients who experienced at least one of the events above by day+15 from treatment start.

- Reduction in the progression to acute respiratory failure [Time Frame: 28 days].
- Overall survival and all-cause mortality (day 15, day 28).
- Time to improvement in oxygenation for at least 48 hours. Improvement in oxygenation is defined as an increase in PaO₂/FiO₂ of 50 (or greater) compared to the nadir of PaO₂/FiO₂.
- Number of patients requiring mechanical ventilation, if not on mechanical ventilation at study entry.
- Change in the WHO COVID-19, “8-point ordinal scale” from study entry to day 28 (Table 1). To be assessed on day 3, day 8, day 15, day 28.
- Duration of hospitalization and duration of ICU care.
- Toxicity assessment (including incidence of grade 3-5 hemorrhagic events).
- Change in D-dimer [Time Frame: baseline, study day 3, day 8, day 15, and day 28]. Changes in plasma D-dimer level compared with baseline at enrollment.
- Decrease or Change in IL-6:IL-10 ratios.
- Free-Days- at day 28
 - Oxygen
 - Ventilator
 - Vasopressor
 - ICU
 - Hospitalization

Table 1: WHO Ordinal Scale Ordinal Score

Patient State	Descriptor	Score
Ambulatory	No limitation of activities	1
	Limitations of activities	2
Hospitalized (mild disease)	No oxygen therapy	3
	Oxygen by mask or nasal prongs	4
Hospitalized (severe disease)	Non-invasive ventilation or high-flow oxygen	5
	Intubation and mechanical ventilation	6
	Mechanical ventilation + additional organ support – pressors, RRT, ECMO	7
Dead	Death	8

Exploratory Endpoints

- Soluble E-selectin and P-selectin levels compared with baseline at enrollment.
- Thrombosis free days (clinically defined) at day 28.
- Change in other cytokine levels, endothelial or leukocyte activation (day 1, 15, 28) in IL-6, IL-10, Angiopoietin-2, and TNF-alpha

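### Oxygen-free days to Day 28 is a secondary endpoint, but the assessment schedule cannot produce it, because oxygen use is not required to be recorded after discharge or on most inpatient days after Day 8

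*Combined protocol and SAP*

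**What the plan says.** Section 3.2 lists "Free-Days- at day 28" with oxygen as the first item, and Sections 5.2.1 and 12.1.3 repeat it. Section 2.2 has the matching objective: "To assess ventilator-free days, ICU-free days, oxygen, vasopressor free days".

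Oxygen support is recorded through the pulmonary indices. Section 6.1.1 defines these as the level of supplemental oxygen, the "current modality of support (mechanical ventilation, BiPaP, CPAP, nasal cannula, or none") and any chest radiograph results. Note d to Table 4 sets the timing: "Pulmonary indices will be recorded daily until cessation of drug therapy, and again at day 8, 15 and 28 (if a patient remains hospitalized"). It then exempts patients who have gone home: "Patients who are discharged prior to day 15 or 28 do not need to have pulmonary indices assessed on day 15 or 28".

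Note f provides a remote contact on Days 15 and 28 (±2 days) "to assess their clinical status and any active adverse events at that time". It does not name oxygen use.

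No section defines an oxygen-free day or says how days after discharge are counted. Section 12.3 says only that the remaining secondary endpoints will be collected and assessed.

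**The concern.** A free-day endpoint needs the status of every day in its window. Here the window runs to Day 28, but the item that carries oxygen status stops at discharge and is intermittent in hospital after Day 8. Inclusion criterion 5 requires supplemental oxygen at entry, so some patients going home on oxygen is foreseeable.

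For such a patient the analyst has two options. The days after discharge can be left missing, or discharge can be read as the end of oxygen and the days counted as oxygen-free. Under the second option the endpoint partly measures how readily the hospital discharges patients on oxygen, rather than how soon they come off it. The choice would be made after the data are seen, and home-oxygen use that nobody asked about may not be recoverable later. Section 12.2 expects this pilot to inform the design of later studies, and an oxygen endpoint with this fault would be a poor basis for that.

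**Working it through.** The documents give no expected value, standard deviation or power for oxygen-free days, so there is no figure to reproduce. The check counts scheduled records and then bounds the endpoint for a patient discharged on oxygen.

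**Inputs**
- Window: Days 1-28 (Sections 3.2 and 5.5).
- Dosing: Days 1-7, given by nurses in the inpatient unit (Sections 5.1.1 and 5.4).
- Pulmonary indices: daily to the end of drug therapy, then Days 8, 15 and 28 if still hospitalized (Table 4, note d).
- Treated patients: 15 (Section 12.2).
- Home-oxygen rate and discharge days: not given.

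**Step 1. Scheduled oxygen records for a patient in hospital throughout.** With a full course these are Days 1-8 plus Days 15 and 28: 8 + 2 = 10 of 28 days. The days without a record are 9-14 (6 days) and 16-27 (12 days): 6 + 12 = 18. The WHO scale also separates oxygen levels for inpatients, but its post-baseline assessment days ("To be assessed on day 3, day 8, day 15, day 28") all fall on days already covered, so it adds none.

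**Step 2. A patient discharged on oxygen.** Assume that oxygen was in use up to and including the day of discharge, Day d. The days after discharge number 28 − d. The lower bound counts all of them as on oxygen (0 oxygen-free days), and the upper bound counts all of them as oxygen-free (28 − d). The largest effect of one such patient on the treated-arm mean is (28 − d)/15.

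| Discharge day | Scheduled records | Undetermined days | Possible oxygen-free days | Largest shift in the mean, one patient |
|---|---|---|---|---|
| 9 | 8 | 28 − 9 = 19 | 0 to 19 | 19/15 = 1.27 |
| 15 | 9 | 28 − 15 = 13 | 0 to 13 | 13/15 = 0.87 |
| 20 | 9 | 28 − 20 = 8 | 0 to 8 | 8/15 = 0.53 |

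Day 9 is used as the early case because discharge before the end of Day 7 would mean an incomplete course of inpatient dosing.

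**Step 3. Several such patients.** With discharge on Day 9: two patients, 2 × 19/15 = 2.53 days; three, 3 × 19/15 = 3.8 days; five, 5 × 19/15 = 6.33 days. These are worst cases. They are reached only if every affected patient stays on oxygen to Day 28 and every one of those days is counted as oxygen-free.

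**Step 4. Can the note f contacts fill the gap?** They ask for status at the time of contact. Even if staff noted current oxygen use, two points in time do not date the end of oxygen use, so the day count stays open unless a stop date is asked for.

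**The case against.** The strongest reply is that this is a missing definition rather than a biased rule, in one of five free-day measures among many secondary endpoints of an unpowered safety pilot. The two secondary endpoints that Section 12.3 singles out, Day 28 survival and Day 28 ventilator-free survival, do not depend on home oxygen. That stands, and it limits the weight of the point.

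A reader might infer more than the documents support:
- **That no oxygen information can exist after discharge.** Note d says that the indices are not needed, not that they are forbidden, and a clinical-status contact could pick up current oxygen use. The gap is that nothing requires it and no stop date is sought.
- **That discharge on oxygen is scored as recovery.** Recovery is not a defined term in the plan, and no rule counts days after discharge as oxygen-free. They could equally be left missing.
- **That the result is tilted in favour of uproleselan.** Counting home-oxygen days as oxygen-free raises the treated-arm figure. Against controls no direction is shown: no between-group analysis of oxygen-free days is specified, and the synopsis defines controls of similar severity from the same period, to whom the same convention could apply.
- **That the WHO scale is at fault.** In Table 1 the ambulatory levels mention only activity ("Limitations of activities" for score 2), so a patient at home on oxygen would be scored 1 or 2. That is the scale applied as printed. A footnote reporting discharge on oxygen separately is optional and is not part of this correction.

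**Conclusion.** As written, the schedule cannot yield oxygen-free days to Day 28. It requires no oxygen record after discharge, and a patient in hospital throughout has a scheduled record on only 10 of 28 days. The inpatient gap can be closed from the chart, although the plan does not say so. The post-discharge gap needs a question that the plan does not ask.

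The size depends on how many patients go home on oxygen and for how long, which the documents do not state. For discharge on Day 9, the undetermined part is up to 1.27 days on the 15-patient mean per patient, and up to 3.8 days for three. It is smaller with later discharge or earlier weaning. The consequence is an endpoint that is uncomputable or partly driven by discharge practice; a bias of known direction against controls is not established. The point concerns a descriptive secondary endpoint and leaves the primary safety endpoint untouched, but the change is cheap and should be made before follow-up data are collected.

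**What to change.** 1. At the existing Day 15 and Day 28 contacts, record whether the patient is or was on home oxygen since discharge and, if it has ended, the stop date.
2. Define the endpoint in Section 12.3 and count each day on home oxygen as not oxygen-free.
3. Name the hospital chart as the source for inpatient Days 9-14 and 16-27.
4. For any comparison with the retrospective controls, use one source in both groups, for example oxygen ordered at discharge, if the de-identified records contain it. Use patient-reported stop dates only to describe the treated arm.

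The cost is one question at two remote contacts already planned, a CRF field, a counting rule and some chart abstraction. There is no added visit and no change to care. The downsides are that stop dates will be patient-reported and that control data may be limited; if the records do not show discharge oxygen, the comparison on this endpoint should not be made.

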8.2 Definitions

8.2.1 Adverse Event Reporting Requirements

Purpose: Adverse event data collection and reporting, which are required as part of every clinical trial, are done to ensure the safety of patients enrolled in the studies as well as those who will enroll in future studies using similar agents.

Adverse Event Reporting:

The descriptions and grading scales used in the revised NCI Common Terminology Criteria for Adverse Events (CTCAE) version 5.0 will be utilized for AE reporting. The CTCAE v5.0 mapping document can be downloaded at the CTEP website:

(https://ctep.cancer.gov/protocoldevelopment/electronic_applications/docs/CTCAE_v5_Quick_Reference_5x7.pdf)

Reporting requirements may include the following considerations: 1) the characteristics of the adverse event including the grade (severity); 2) the relationship to the study therapy (attribution); and 3) the prior experience (expectedness) of the adverse event.

Adverse events (AE) refer to any untoward medical occurrence associated with the use of an intervention in humans, whether or not considered intervention-related (21 CFR 312.32 (a)). By way of example and without limitation, an AE can be any unfavorable and unintended sign (for example, an abnormal laboratory finding), symptom, or disease temporally associated with the use of the Study Drug.

Protocol-defined and serious AE will be collected for 28 days following the first study drug dose, or death, whichever comes first. In addition, patients with drug related AE will be monitored until symptom resolution, even if the symptoms extend beyond the 28-day period.

AEs may include:

- Exacerbation (i.e., an increase in the frequency or severity) of a pre-existing condition. Illness present before study entry should be recorded in the medical history section of the CRF and only be reported as an AE if there is an increase in frequency or severity of the condition during the study.
- Intercurrent illnesses with an onset after administration of study drug begins.

AEs DO NOT include:

- Any medical condition or laboratory abnormality with an onset date before initial study treatment is considered to be pre-existing in nature. Any known pre-existing conditions that are ongoing at time of study entry should be considered medical history.
- Medical or surgical procedures (the condition that leads to the procedure is the AE)
- Situations where an untoward medical occurrence has not taken place. For example:

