12.3 Data Analyses Plans

Descriptive statistics will be calculated for quantitative safety data, as well as change from baseline. Frequency counts will be compiled for classification of qualitative safety data.

Secondary endpoints include reduction in the progression to acute respiratory failure. For patients with a baseline PaO₂/FiO₂ \geq 200: progression of respiratory failure is defined by:

- severe gas transfer deficit (PaO₂/FiO₂ < 200);
- persistent respiratory distress while receiving oxygen (persistent marked dyspnea, use of accessory respiratory muscles, paradoxical respiratory movements);

The rate will be calculated as the proportion of patients who experienced at least one of the events above by day+15 from treatment start.

There are many other secondary endpoints, but two of the most important are: (i) Day 28 overall survival and (ii) Day 28 ventilator free survival, both of which are binary endpoints. Day 28 overall survival will be summarized by the proportion of the twelve patients who are alive at Day 28 after starting treatment, and Day 28 ventilator-free survival will be summarized by the proportion of the twelve patients who are both alive and not using a ventilator at Day 28 after starting treatment. Both proportions will be

accompanied by an exact 95% confidence interval. All other secondary endpoints will be collected and assessed.

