13 STUDY STOPPING RULES

Additional Interim Safety Assessment (Study Sample Size: 15 patients)

An interim assessment for toxicity and early mortality will be performed after the first 5 patients have enrolled, and again after the first 10 patients are enrolled. Accrual may proceed to a maximum of 15 patients, if the stopping rules are not met within the first 5 patients

The study may be halted for further review if, for any reason involving subject safety, the PIs and Medical Monitors deem continuing the study inappropriate. The following scenarios will also result in temporarily halting the study for further review: 1) major bleeding event in more than 2 of first 10 patients on protocol (as defined as fatal bleeding and/or symptomatic bleeding in a critical area or organ, such as intracranial, intraspinal, intraocular, retroperitoneal, intraarticular or pericardial, or intramuscular with compartment syndrome and/or bleeding causing a fall in hemoglobin level of 2g/dL or more, or leading to transfusion of two or more units of whole blood or red cells). This bleeding definition is congruent with International Society of Thrombosis and Hemostasis (ISTH) definition of major bleeding. An incidence of > 20% hemorrhagic complications would be unacceptable in this setting. Thus, we will continually monitor the observed proportion of patients with major bleeding complications. We start with prior Beta distribution, which has mean 0.2. If ever we have more than 80% posterior probability that the true proportion is greater than 0.20, accrual to the protocol will be suspended to allow the MM and PIs to review the incidence of major bleeding. 2) We will also continually monitor the study for excessive Day 15 mortality. In parallel with our decision rule related to excessive severe hemorrhagic events, we will suspend accrual if we see if we see at least five deaths by Day 15 among the first six patients, or at least seven deaths by Day 14 among the first eleven patients. If the true Day 14 mortality rate is 70% (which is the historical rate for patients with respiratory compromise), the study has a probability of 0.80 of being suspended. Conversely, if the Day 14 mortality rate is 50%, the study has a much lower probability of 0.30 of being suspended.

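### The final remote contact may be made on Day 26, before the 28-day adverse event window and the Day 28 survival endpoints it has to serve

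*Combined protocol and SAP*

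**What the plan says.** Section 6.2, Table 4 note f, provides for two remote contacts: "patients will be contacted on day 15 and 28 (± 2 days), to assess their clinical status and any active adverse events at that time". It continues: "This final assessment can be done virtually, by telephone or electronically (email) if the patient cannot be contacted by phone". Note f also has adverse events assessed daily during treatment and "for 7 days following completion of study drug therapy, provided they remain hospitalized during this 7-day post-therapy period". Table 4 marks an adverse event assessment on Day 8 as well. Notes d and g release discharged patients from the Day 15 and Day 28 pulmonary indices and rule out outpatient study blood draws.

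Section 8.2.1 sets the collection period: "Protocol-defined and serious AE will be collected for 28 days following the first study drug dose, or death, whichever comes first". Beyond that, "patients with drug related AE will be monitored until symptom resolution, even if the symptoms extend beyond the 28-day period". Section 5.5 gives 28 days of follow-up.

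Section 12.3 singles out two binary endpoints. For the first, "Day 28 overall survival will be summarized by the proportion of the twelve patients who are alive at Day 28 after starting treatment"; the second is being alive and off a ventilator on that day. Section 13 adds: "We will also continually monitor the study for excessive Day 15 mortality".

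**The concern.** A symmetric window suits a visit that measures something drifting slowly. It suits less well a contact whose job is to establish whether an event has happened by a fixed day, because the early half of the window falls before that day. For a patient who has gone home, the two remote contacts are the only follow-up described after Day 8. If the second is made on Day 26 or 27, the site has complied with the schedule, yet nobody is scheduled to learn what happens up to Day 28.

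At stake are the tail of the safety window, in a study whose primary endpoint is safety, and the Day 28 status of a patient in a cohort small enough for one patient to matter. Note f also asks for status and active events as they are when the contact is made, not as of the nominal day. An early answer therefore would not correct itself.

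**Working it through.** The plan gives no figure of its own to reproduce here; the check is a day count.

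**Inputs**
- Contact tolerance: 2 days either side (Table 4 note f).
- First dose: Day 1 (Section 5.4, treatment days 1-7).
- Collection period: 28 days following the first dose (Section 8.2.1).
- Analysis day for the two survival endpoints: Day 28 (Section 12.3).
- Treated patients: 15 (Sections 12.1 and 12.2). Section 12.3 uses twelve as the denominator for these proportions, so both are shown.

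**Earliest compliant contact** = nominal day - 2. For the final contact, 28 - 2 = Day 26. For the Day 15 contact, if the tolerance applies to it, 15 - 2 = Day 13.

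**Uncovered days** = last day of the window - contact day. The last day depends on how the 28 days are counted.

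| Final contact | Window closes Day 28 (Day 1 is the first day) | Window closes Day 29 (28 full days after Day 1) |
|---|---|---|
| Day 26 | 2 days, 2/28 = 7.1% | 3 days, 3/28 = 10.7% |
| Day 27 | 1 day, 3.6% | 2 days, 7.1% |
| Day 28 | 0 | 1 day, 3.6% |
| Day 29 or 30 | 0 | 0 |

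On the second count, even a contact exactly on Day 28 is one day short.

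**What else could cover the gap.** Daily assessment after treatment runs to Day 7 + 7 = Day 14 when dosing ends on Day 7, and only for inpatients. Monitoring past the window is specified only for drug-related events. No repeat contact, record check or vital-status check on or after Day 28 is scheduled for discharged patients.

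**Weight of one unseen death** (illustration with exact Clopper-Pearson 95% intervals, not an estimate of bias)
- Of 15: 15/15 = 100% (78.2 to 100%) would be reported where the truth is 14/15 = 93.3% (68.1 to 99.8%), a difference of 1/15 = 6.7 points.
- Of 12: 12/12 = 100% (73.5 to 100%) against 11/12 = 91.7% (61.5 to 99.8%), a difference of 1/12 = 8.3 points.

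**Day 15, if the tolerance applies there.** After a Day 13 contact, a death on Day 14 or 15 might first surface at the next scheduled contact, on Days 26-30. Shortest delay: 26 - 15 = 11 days. Longest: 30 - 14 = 16 days.

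**The case against.** The strongest reply is that note f waives nothing. Section 8.2.1 requires collection to 28 days and Section 5.5 follow-up to 28 days. Sections 8.2.2 and 8.4 require serious events to be reported within 24 hours of first awareness, whenever that comes. A reader might infer that an early contact ends the collection of serious events. The documents do not say so, and that part of the reply stands. What remains is narrower: the duty exists, but reporting depends on awareness, and no scheduled contact creates awareness after Day 26.

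A reader might also infer that every resulting error favours the drug. That is so for deaths, since a patient reached alive on Day 26 can only be wrongly counted as a survivor. It is not so for ventilation. A readmitted patient on a ventilator at a Day 26 contact and off it by Day 28 would be counted as a failure in error.

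The Day 15 argument is the weakest. The tolerance is written directly after the Day 28 contact and the next sentence speaks of one final assessment, so it may not apply to Day 15 at all. If it does, the final contact can still recover Day 15 status, so the loss is of time and not of data. The mortality rule in Section 13 needs five deaths among six patients or seven among eleven, and Section 14 provides ongoing review of serious events and monthly meetings. A reader might infer that an early contact defeats this rule. The documents support only a possible delay.

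Finally, the gap affects only discharged patients contacted early, for 2 or 3 days. This stands and limits the size of the point, but does not remove the mismatch.

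**Conclusion.** The point holds as a mismatch between the contact schedule and the windows it serves. A fully compliant site can make its last scheduled contact with a discharged patient 2 days (7.1%) before the adverse event window ends on a Day 28 count, or 3 days (10.7%) on a Day 29 count, and before both highlighted survival endpoints are reached. The wording of Section 8.2.1 does not settle which count is meant.

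The practical effect is probably small. It needs a discharged patient, an early contact and an event in the remaining days; the documents give no rate for this, and low is an assumption. If the event were an undetected death, Day 28 survival would be overstated by 6.7 points on 15 patients or 8.3 points on twelve. Ventilator status could err either way. For Day 15 the consequence is conditional on how the tolerance is read, and is an 11 to 16 day delay to monitoring that is meant to be continual. The case for acting rests on the low cost of the change, not on a demonstrated bias.

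**What to change.** In Table 4 note f, make the final contact one-sided: no earlier than Day 28 (0 to +2 days). If the collection period is meant as 28 full days after a Day 1 dose, make it no earlier than Day 29. State which count applies and align Table 4 with Sections 5.5 and 8.2.1. A Day 28 limit leaves 0 days uncovered on the first count and 1 day on the second; a Day 29 limit leaves 0 on both. Make the Day 15 contact 0 to +2 days, which also removes the doubt over where the tolerance applies.

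On the contact form, record vital status, ventilation and hospitalisation as of Day 15 or Day 28, whatever the date of the call, together with all adverse and serious adverse events since the previous contact, with event dates.

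No contacts are added. The cost is slightly less scheduling flexibility, a few fields on the contact form and, under the Day 29 option, matching edits to the Day 28 column of Table 4 and to the follow-up period in Section 5.5. The Day 28 option needs less change and is enough for the survival endpoints.
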